7.4 Monitoring for antihypertensive withdrawal

All patients will be closely monitored for sudden rise in blood pressure following dose reduction or withdrawal of antihypertensive drugs. Patients will be educated about warning symptoms such as headache, palpitations, chest pain, breathing difficulty and to immediately report to the treating physician. Also home based blood pressure monitoring will be done twice daily

7.5 Blood pressure monitoring

For the study both Home based monitoring, Ambulatory Blood pressure monitoring, and Clinic based blood pressure monitoring will be used. While ambulatory blood pressure

monitoring and clinic based blood pressure will be primarily used for end point assessment, home based blood pressure monitoring will be used for dose titration and safety monitoring.

7.5.1 Ambulatory blood pressure monitoring

For all patients ambulatory blood pressure monitoring will be done at monthly intervals for the first 3 months followed by every 3 months till the end of study and also as required by the primary treating physician.

Each measurement will be done for 24 hours. The following criteria will be used for adequacy of measurement (O'brien et al)

- 24 hr reading with > 70% of expected measurements
- 20 valid awake readings
- 7 valid readings at sleep

The frequency of measurement will be half hourly in day time and hourly at night time. Day time and sleep time will be defined based on the sleep time reported by the patient. Activity of the patient along with the time of food intake and medications will be captured during the ambulatory blood pressure monitoring.

7.5.2 Home based blood pressure monitoring

- Home based monitoring of blood pressure will be done using a calibrated Omron automatic blood pressure monitoring device. Purpose of home based BP monitoring is to ensure early detection of patients with extremes of blood pressure and to regulate the dose of antihypertensive medications.
- Blood pressure will be taken the same time each day in a comfortable room and sitting position after resting for at least 5 minutes.
- Patients will be instructed to avoid any stimulants such as coffee, tea, smoking or exercise 30 to 60 minutes before the measurement. Frequency of home-based monitoring will be twice a day daily for 5 days every week before taking medications (trough level) throughout the study period

7.5.3 Clinic based blood pressure monitoring

- Clinic based blood pressure assessment will be done by a trained nurse/doctor at the time of each study visit in both the groups.

Instructions to be followed while measuring blood pressure

- Blood pressure should be measured in a comfortable room and sitting position after resting for at least 5 minutes.
- At the time of initial evaluation measure BP in both the arms. If the difference between both the arms is > 10 mm Hg use the arm with the higher measurements. If the difference is > 20 mm Hg consider further evaluation.

- The same arm should be used preferably for all subsequent BP measurements.
- Take 3 readings at an interval of 1 min and the average of the last 2 measurements should be taken
- Patients should be instructed to avoid any stimulants such as coffee, tea, smoking or exercise 30 to 60 minutes before the measurement. Instruct the patient to empty the bladder.

7.6 Patient follow up and study period:

Patients will be followed up one month after randomisation followed by every 3 months till the end of 2 years or patient withdrawal. Details of the schedule of assessment is included in annexure

8. Schedule of activities assessment (refer annexure)

9. Study endpoints & outcomes

9.1 Primary endpoint

1. Primary outcome will be change in blood pressure as measured by ambulatory blood pressure monitoring at the end of 1 year
2. Primary outcome will be a change in blood pressure as measured in the clinic at the end of 1 year

Ambulatory blood pressure monitoring

Measurements will include mean 24h systolic and diastolic pressures, and daytime values (measured every 30 min from 07:00 am to 10:00 pm) and night-time values (measured every 60 min from 10:00 pm to 07:00 am). Only ambulatory BP recordings with a minimum of 70% measurements will be considered as successful.

In Clinic or office blood pressure: Average of 3 readings measured in the morning with 1 min gap at baseline and end of the study will be considered. Procedure for measurement of blood pressure is detailed under section 6.5 Blood pressure monitoring

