4.1. Primary Objective

1. To compare the mean change in systolic and diastolic 24 hr blood pressure ambulatory from baseline to 1 year between the 2 groups
2. To compare the mean change in systolic and diastolic blood pressure clinic based from baseline to 1 year between the 2 groups

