Moderation of alcohol consumption and smoking cessation	
Counselling will be provided on the importance of cessation of smoking and alcohol consumption. Habitual drinkers will be advised on the moderation of amount and to avoid binge drinking. The recommended daily limit for alcohol consumption is 2 standard drinks for men and 1.5 for women (10 g alcohol/standard drink).

Management of blood pressure in standard care arm

Medication will be started or up titrated if blood pressure is > 140/90 mm Hg and treated to reach target blood pressure

Target blood pressure control will be(10)

Office

- In <65 years < 130/80 mm Hg
- In 65 and above < 140/90 mm Hg

ABPM

- 24 hr average \leq 130 and/or \leq 80
- Day time average \leq 135 and/or \leq 85
- Night time average \leq 120 and/or \leq 70

HBPM \leq 135 and/or \leq 85

Frequency of assessment: For patients in the standard care arm, blood pressure will be assessed monthly after initiation or change in antihypertensive medication until target blood pressure is reached. Subsequently blood pressure will be monitored every 3 monthly.

Standard care home based BP monitoring: Self-measured BP monitoring be based on 2 measurements taken at least 1 minute apart in the morning and evening (ie, 4 readings per day) optimally for 7 days (ie, 28 readings total) with a minimum of 3 days (ie, 12 readings total). For each monitoring period, the average of all SBP and DBP readings should be obtained to assess BP. If the first day's readings are excluded, the preferred and minimum periods of monitoring should be 8 and 4 days, respectively. (9)

Standard care Office based BP monitoring:y 2–3 office visits at 1–4-week intervals. At each visit take 3 measurements with 1 min between them. Calculate the average of the last 2 measurements. If BP of first reading is <130/85 mmHg no further measurement is required.(10)

Stepwise approach for use of antihypertensive medications

Consider monotherapy in low risk grade 1 hypertension or in very old (> 80 yrs).

Category	Systolic		Diastolic
Normal BP	<130	and	<85
High normal BP	130-139	and/or	85-89
Grade 1 hypertension	140-159	and/or	90-99

Grade 2 hypertension	≥ 160	and/or	≥ 100
----------------------	-------	--------	-------

Table-1 Grades of hypertension

Classification of hypertension risk based on risk factors, end organ damage. (Table-2)

Risk factors/ Hypertension mediated organ damage	High normal blood pressure	Grade 1 hypertension	Grade 2 hypertension

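### The clinic BP primary endpoint has two averaging rules and two time points, and a single-reading shortcut written for one arm is not excluded at endpoint visits

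*Protocol*

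**What the plan says.** **Time point.** Section 4.1 sets the objective: "To compare the mean change in systolic and diastolic blood pressure clinic based from baseline to 1 year between the 2 groups". Item 2 of section 9.1 agrees: "Primary outcome will be a change in blood pressure as measured in the clinic at the end of 1 year". The synopsis and the sample size calculation in 12.1 also use 1 year. The measurement paragraph of 9.1 differs: "Average of 3 readings measured in the morning with 1 min gap at baseline and end of the study will be considered". Section 5 gives a 2-year intervention period and a total of about 3 years including passive follow-up. Section 9.2 lists change at 2 years as a separate secondary outcome.

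**Averaging.** The same sentence of 9.1 averages all 3 readings. Section 7.5.3 says: "Take 3 readings at an interval of 1 min and the average of the last 2 measurements should be taken". Its scope is explicit: "Clinic based blood pressure assessment will be done by a trained nurse/doctor at the time of each study visit in both the groups". Section 7.5 confirms that this is the endpoint measurement: ambulatory "monitoring and clinic based blood pressure will be primarily used for end point assessment".

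**Single reading.** Section 7.3.1, in its paragraph on office monitoring in standard care, gives the last-2 rule ("Calculate the average of the last 2 measurements") and then adds: "If BP of first reading is <130/85 mmHg no further measurement is required". No matching sentence is written for the intervention arm in 7.3.2.

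**Cross-reference.** For the procedure, 9.1 points to a section 6.5 titled Blood pressure monitoring. The section with that title is 7.5.

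**The concern.** A primary endpoint needs one definition, applied in the same way in both arms. Here the same three readings give two different values, depending on whether 9.1 or 7.5.3 is followed. Repairing the cross-reference does not help, because it leads to 7.5.3, the rule that contradicts 9.1. The conflict also spreads: 9.2 says that the 6-month and 2-year pressures are measured as in the primary endpoint.

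The shortcut in 7.3.1 is a separate problem. If a nurse follows it at the 1-year visit of a standard-care patient, readings 2 and 3 are never taken and no later analysis rule can recover them. The choice between averaging 3 and averaging 2 can be settled afterwards, but only if all three readings were taken and recorded individually.

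**Working it through.** **Reference figure.** Section 12.1 plans for a 5 mm Hg difference in systolic reduction, SD 13, 80% power, 5% alpha (12.2: two-tailed) and 1:2 allocation. The normal approximation gives 1.5 × (13 × (1.960 + 0.842) / 5)² = 79.6, so 80 and 160. The t-based calculation gives 80.2, so 81 in the smaller arm. The stated 83 and 166 are slightly conservative (power 81.6%). Dropout: 83 / 0.8 = 103.75, so 104; 166 / 0.8 = 207.5, so 208. The present point changes none of these figures. The 5 mm Hg serves only as a yardstick, and 12.1 does not say whether it refers to clinic or ambulatory pressure.

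**Mean of 3 against mean of the last 2.** Let the last two readings average m and the first be m + d. The documents give no value for d. The mean of 3 is (m + d + 2m) / 3 = m + d/3, so the two rules differ by d/3.

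| assumed d (mm Hg) | d/3 (mm Hg) | share of 5 mm Hg |
|---|---|---|
| 2 | 0.67 | 13% |
| 4 | 1.33 | 27% |
| 6 | 2.00 | 40% |
| 8 | 2.67 | 53% |

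With one rule at all visits in both arms, most of this drops out of the between-arm difference in change. If the arms use different rules at 1 year, the full d/3 enters that difference. If the rule switches between baseline and 1 year, each arm's change is off by d/3, and this drops out of the comparison only if the switch is equally common in both arms.

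**Single-reading shortcut, systolic only.** Take a patient whose later readings average μ, with a first reading of mean μ + d and SD s. The value kept is the first reading if it is below 130, and otherwise the mean of the last 2. The expected shift against always using the last 2 is d·Φ(z) − s·φ(z), with z = (130 − μ − d)/s. Assumed: s = 4 to 7, d = 4 to 8.

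- μ = 130, s = 4: z = −1 at d = 4 gives 4 × 0.159 − 4 × 0.242 = −0.33; z = −2 at d = 8 gives −0.03.
- μ = 130, s = 7: −1.24 at d = 4 and −0.44 at d = 8.
- μ = 118: +2.0 (s = 7, d = 4) to +5.8 (s = 4, d = 8).

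**Averaged over patients.** Simulation with assumed between-patient SD 13 and reading error SD 5, systolic only:

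| mean SBP | d = 0: shift (share stopping) | d = 6: shift (share stopping) |
|---|---|---|
| 130 | −0.71 (50%) | +1.34 (33%) |
| 135 | −0.67 (36%) | +0.77 (21%) |
| 140 | −0.56 (24%) | +0.38 (13%) |

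The sign depends on d. The diastolic condition (below 85) would reduce the share stopping.

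**The case against.** The shortcut in 7.3.1 is not an endpoint definition. It is permissive and conditional, it sits in text on managing standard care, and otherwise it agrees with 7.5.3. Baseline is measured before randomisation (7.1), so an arm-specific rule cannot define it. This stands: the endpoint has two competing averaging rules, not three. What remains is that no text exempts endpoint visits.

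A reader might infer that keeping a single reading only when it is low must lower standard-arm pressure and so work against the intervention. With no first-reading excess, the shift at a true value of 130 is −s·φ(0), or −1.6 to −2.8 mm Hg for s = 4 to 7. That sets d to zero, whereas the d/3 argument needs d above zero. With both in one formula the sign is not fixed, and no direction can be claimed.

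It is also fair to say that 1 year is stated so consistently that hardly anyone would analyse year 2 or 3 as primary, and that the 6.5 reference is a numbering slip, since the title identifies 7.5. Both stand. The reference to study end is stray wording to be corrected, not a real doubt about the time point. Finally, the ambulatory primary outcome is not affected by any of this.

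**Conclusion.** The contradiction holds for the clinic BP primary outcome: 9.1 and 7.5.3 average different readings, and the measurement sentence in 9.1 names a time point that conflicts with the rest of the protocol. Under an assumed first-reading excess of 4 to 8 mm Hg, the averaging rules differ by 1.3 to 2.7 mm Hg. This is the error at stake if the rules are mixed by arm or between baseline and 1 year, not a bias that the trial is shown to have. The one-arm shortcut adds a possible between-arm measurement difference. Its average size in the simulated settings is −0.7 to +1.3 mm Hg, so its direction is uncertain. All these sizes rest on assumed within-visit behaviour; the textual conflict does not. This is an open-label trial and readings not taken cannot be recovered, so the text should be settled before endpoint visits are measured.

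**What to change.** In 9.1, define clinic BP as the mean of the last 2 of 3 readings, as in 7.5.3, for both arms at baseline and 1 year, and likewise at the 6-month and 2-year secondary time points. Require all 3 readings at these visits. State that the single-reading shortcut in 7.3.1 does not apply to endpoint measurements; its use in routine standard-care monitoring need not change. Replace the reference to the end of the study by 1 year, and correct the cross-reference to 7.5.3. The cost is a few words, plus about two extra minutes at those endpoint visits where measurement would otherwise have stopped after one reading. The sample size is unchanged.

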9.2 Secondary outcome

Blood pressure and antihypertensive medication related

1. **Change in blood pressure (Clinical and ambulatory blood pressure)** from baseline to 6 months and 2 year. Ambulatory and clinic blood pressure monitoring will be done as mentioned in the primary endpoint.
2. **Adequate control of blood pressure** as measured by ambulatory blood pressure monitoring at 1 year and 2 years

Criteria for adequate control of blood pressure is

- In <65 years < 130/80 mm Hg
- In 65 and above < 140/90 mm Hg

3. Number of antihypertensive medications at 6 months, 1 year and 2 years

Among those with adequate control, the number of antihypertensive medications will be calculated at baseline (after run in period) and subsequently every 3 months. Combination pills containing more than one group (of antihypertensive medications) will be considered based on the number of groups. Example: Lotrel which is a combination of Amlodipine and benazepril will be considered as 2 drugs. Further each drug will be categorized as high dose or low dose.

Table-5 for doses of commonly used antihypertensive medications

Drug name	Dose 1	Dose 2	Dose 3	Dose 4
Losartan	25 mg	50 mg		
Telmisartan	20 mg	40 mg	80 mg	
Olmesartan	5 mg	20 mg	40 mg	
Candesartan	16 mg	32 mg		
Captopril	12.5 mg	25 mg	50 mg	100 mg
Enalapril	5 mg	10 mg	20 mg	40 mg
Lisinopril	5 mg	10 mg	20 mg	40 mg
Ramipril	1.25 mg	2.5 mg	5 mg	
Hydrochlorothiazide	12.5 mg	25 mg	50 mg	100 mg

Chlorthalidone	25 mg	50 mg	100 mg	
Indapamide	1.25 mg	2.5 mg	5 mg	
Frusemide	20 mg	40 mg		
Prazosin	1 mg	2.5 mg	5 mg	
Terazosin	1 mg	2 mg	5 mg	
Doxazosin	1 mg	2 mg	4 mg	
Propranolol	10 mg	20 mg	40 mg	
Metoprolol	25 mg	50 mg	100 mg	
Atenolol	50 mg	100 mg		
Bisoprolol	5 mg	10 mg		
Amlodipine	5 mg	10 mg		
Cilnidipine	5 mg	10 mg	20 mg	
Nicardipine	20 mg	40 mg	80 mg	
Nifedipine	30 mg	60 mg	90 mg	
Felodipine	2.5 mg	5 mg	10 mg	

4. Frequency of introduction of new antihypertensive medications or dose increment of existing antihypertensive medications will be noted across both the groups and compared.

Metabolic parameters and biomarkers based

5. Change in metabolic parameters

- Will include anthropometric assessment (Height, Weight, BMI, waist circumference, Waist hip ratio, visceral fat), lipid profile including lipoprotein (a), apolipoprotein - A1, apolipoprotein - B, insulin resistance (measured by HOMA- IR) every 3 months till end of study

6. Change in cardiac and renal biomarkers

- Cardiac biomarkers include Left ventricular hypertrophy (LVH), Ejection fraction

(EF) by Echo; Carotid intimal media thickening (cIMT) and NT pro BNP. All parameters will be measured 3 monthly except cIMT (measured 6 monthly)

- Renal biomarkers include blood urea, serum creatinine, eGFR and albumin creatinine ratio, measured every 3 months till the end of study

Quality of life and Safety related

7. Safety assessment will include

- All reported adverse effects, abnormal changes in blood investigations,
- Frequency of uncontrolled hypertension, hospital admissions due to uncontrolled blood pressure or hypertension related complications

8. Change in quality of life

- **Quality of life will be assessed using SF-36.** SF-36 is an indicator of overall health status. It has eight scaled scores under the following section (vitality, physical functioning, body pain, general health perceptions, physical, emotional and social functioning, mental health) Score ranges from 0-100 with higher score meaning less disability.
- **Physical activity** assessment using International physical activity questionnaire (IPAQ)
- **Treatment satisfaction** will be assessed using the Treatment satisfaction questionnaire for medications (TSQM). TSQM assesses four key dimensions of treatment satisfaction: Effectiveness; Side Effects; Convenience; and Global Satisfaction, enabling comparisons across medication types and diseases.
- **Stress assessment** using Perceived Stress Questionnaire

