4.3 Exploratory objective

1. To study the change in exploratory biomarkers between the 2 groups
 - Endothelial function based biomarkers
 - Stress based biomarkers
 - Inflammatory biomarkers
 - Hormones, Vitamins and minerals
2. To study the incidence of hypertension mediated organ damage (brain, heart, kidney, artery, eyes)

5. Study design: Multi centric, open label, parallel arm randomized controlled trial

[figure not shown]

Figure-1 Study design

Study period: The total study period will be for approximately 3 years as follows:

Run in period: 2-3 weeks

Intervention period: 2 year

Passive Follow up: 1 year

After screening, all eligible patients will have a mandatory 2-3 weeks run-in period with existing therapy (standard care) for stabilization of blood pressure and for baseline continuous glucose monitoring. Patients with blood pressure >180/110 mm Hg at the end of 3 weeks run-in period will be considered as screen failure.

Number of groups:

Group A (Standard care arm): Will receive medications for hypertension along with lifestyle modifications as per existing guidelines

Group B (Intervention arm): Will receive Twin Precision Treatment along with standard care

6. Eligibility criteria

Inclusion criteria

1. Patients with diagnosis of primary hypertension (either adequately controlled or inadequately controlled with blood pressure \leq 180/110 mm Hg); both treatment naive & on treatment (includes monotherapy or multiple drugs)
2. Age 18 years and above
3. Of either gender
4. Willing to follow study specific activities and able to handle smartphone

Exclusion criteria

Patients with the following criteria will be excluded.

1. Uncontrolled hypertension ($>$ 180/110 mm of Hg) or history of hypertensive emergency requiring admission
2. Hypertension due to secondary causes
3. History of Diabetes mellitus (when either of the following criteria is met: on medications to control blood sugar or FBS $>$ 126 mg/dl; RBS $>$ 200 mg/dl; HbA1c \geq 6.5)
4. Symptomatic heart failure or EF $<$ 40%
5. Chronic kidney disease (eGFR less than 60 ml/min/1.73 m²) or history of any major renal anomalies like unilateral kidney, polycystic kidney
6. Any major cardiovascular event in the last 6 months (such as MI, stroke, TIA)
7. Hypertensive Retinopathy (grade 3 and above)
8. Weight loss more than 5% in 3 months
9. Arm circumference too large or small to allow accurate BP measurement with available devices

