Dose reduction or withdrawal of antihypertensive drugs will be considered when the patient reaches the target blood pressure. The dose reduction is in accordance with the protocol described by Nelson et al. i.e half dose reduction at weekly intervals with weekly assessment until the lowest dose is reached followed by withdrawal. The period of withdrawal will range from 2 weeks to 4 weeks.

Target blood pressure for our study will be considered as 130/80 mm Hg for young individuals and 140/90 mm Hg for elderly (65 and above) -2020 International Society for Hypertension Global Hypertension Practice Guidelines

Table-4 Antihypertensive medicines escalation and de-escalation protocol

Tier number	Medicines	Initial condition on enrolment	Reduction condition	Increase conditions
Tier 0	No medicine	Initial no medicine & BP < 160/100 mm Hg		Move to Tier 1, if (5d-BP > 135/85) & (after staying in this tier for 5 days)
Tier 1	Monotherapy (A)	Monotherapy	Move to Tier 0, if ((1d-BP < 135/85 for 7 consecutive days) II (1d-BP < 90/60 for 3 consecutive days) II (Symptoms of Hypotension like Postural Giddiness)) && (EOD-)	Move to Tier 2, if (5d-BP > 135/85) && (after staying in this tier for 5 days)
Tier 2	Dual low dose combination (A+C)	Dual low dose combination	Move to Tier 1, if ((1d-BP < 135/85 for 7 consecutive days) II (1d-BP < 90/60 for 3 consecutive days) II (Symptoms of Hypotension like Postural Giddiness))	Move to Tier 3, if (5d-BP > 135/85) && (after staying in this tier for 5 days)

Tier 3	Dual full dose combination (A+C)	Dual full dose combination/ Triple combination/ Triple combination + spironolactone or Alpha blocker	Move to Tier 2, if ((1d-BP < 135/85 for 7 consecutive days) II (1d-BP < 90/60 for 3 consecutive days) II (Symptoms of Hypotension like Postural Giddiness))	Move to Tier 4, if (5d-BP > 135/85) && (after staying in this tier for 5 days)
Tier 4	Triple combination (A+C+B/ D/ Alpha blocker)	Triple combination/ Triple combination + spironolactone or Alpha blocker	Move to Tier 3, if ((1d-BP < 135/85 for 7 consecutive days) II (1d-BP < 90/60 for 3 consecutive days) II (Symptoms of Hypotension like Postural Giddiness))	Consider manual change of medication or withdraw

A= ACE inhibitor or ARB

C = Calcium channel blocker

B = Beta blocker

D = Diuretics

Note:

- EOD (End organ damage) + =
1. LVH present
 2. Albuminuria
 3. Evidence of Heart failure
 - A. Low ejection fraction
 - B. High pro-BNP
 - C. Clinical features
 4. Hypertensive retinopathy

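### Secondary outcome 2 measures blood pressure control by ABPM but scores it with the protocol's age-split office cut-offs, so patients aged 65 or over can count as controlled above both 24-h ABPM limits

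*Protocol*

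**What the plan says.** Section 9.2, item 2 makes adequate control a secondary outcome, assessed "as measured by ambulatory blood pressure monitoring at 1 year and 2 years". Its criteria are "In <65 years < 130/80 mm Hg" and "In 65 and above < 140/90 mm Hg".

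Section 7.3.1, on management in the standard care arm, gives the same two age-split lines under the label Office. A separate ABPM list follows, with no age split:

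- "24 hr average \leq 130 and/or \leq 80"
- "Day time average \leq 135 and/or \leq 85"
- "Night time average \leq 120 and/or \leq 70"

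The antihypertensive withdrawal protocol in 7.3.2 adds a study-wide statement that names no instrument: "Target blood pressure for our study will be considered as 130/80 mm Hg for young individuals and 140/90 mm Hg for elderly (65 and above".

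The eligibility criteria in section 6 set only a lower age limit ("Age 18 years and above"), so patients aged 65 or over can enrol. Item 3 of 9.2 counts antihypertensive drugs among patients who meet the adequate-control definition.

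**The concern.** The endpoint names one instrument and uses the cut-offs that the protocol assigns to another. From age 65, the cut-off applied to the ambulatory reading is 10 mm Hg higher, for both systolic and diastolic pressure, than the 24-h ABPM limit in 7.3.1. The same recording can be called controlled under one section and above target under another, and nothing in the protocol explains the departure.

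At stake is the meaning of the control proportion, the only such proportion among the 9.2 outcomes. Because item 3 is restricted to patients with adequate control, any misclassification carries into the medication-count result. The primary endpoints and the sample size do not depend on this definition.

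**Working it through.** The protocol states no expected control rate, so there is no figure to reproduce. The check compares the rules and then sizes the gap under stated assumptions.

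**Step 1: the rules side by side (mm Hg)**

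| Age | Endpoint rule, 9.2 item 2 (ABPM) | Office list, 7.3.1 | ABPM 24-h list, 7.3.1 |
|---|---|---|---|
| <65 | <130/80 | <130/80 | ≤130 and/or ≤80 |
| ≥65 | <140/90 | <140/90 | ≤130 and/or ≤80 |

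**Step 2: where the rules disagree.** All whole-number 24-h pairs with SBP 100-160 and DBP 60-110 were classified by the 9.2 rule and by the 24-h ABPM limits. The joining phrase in the ABPM list was read both ways.

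- *Age 65 or over, either limit suffices.* The conflict is SBP 131-139 with DBP 81-89: 9 × 9 = 81 pairs. Both limits are exceeded, so even the lenient reading does not remove it.
- *Age 65 or over, both limits required.* The 9.2 rule accepts 40 × 30 = 1,200 pairs on the grid and the ABPM limits accept 31 × 21 = 651. The conflict is 1,200 − 651 = 549 pairs.
- *Age under 65.* No pair is controlled under 9.2 and above the 24-h limits. With both limits required, the only differences are values of exactly 130 or exactly 80 (< against ≤).
- *Daytime mean instead of 24-h, age 65 or over.* Pairs from 136/86 to 139/89 still pass 9.2 and exceed both daytime limits of 135/85.

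These counts show where the rules disagree. They are not patient frequencies.

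**Step 3: how many older patients could be affected.** The protocol gives no 24-h distribution, so a normal 24-h SBP with mean m and SD s is assumed. The share between 130 and 140 is Φ((140 − m)/s) − Φ((130 − m)/s).

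| m | s = 10 | s = 13 |
|---|---|---|
| 120 | 0.977 − 0.841 = 0.136 | 0.938 − 0.779 = 0.159 |
| 125 | 0.933 − 0.691 = 0.242 | 0.876 − 0.650 = 0.226 |
| 130 | 0.841 − 0.500 = 0.341 | 0.779 − 0.500 = 0.279 |
| 135 | 0.691 − 0.309 = 0.383 (before rounding) | 0.650 − 0.350 = 0.299 (before rounding) |

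The range is about 14% to 38% of those aged 65 or over. If 20-30% of patients are in that age group (also assumed), the overall shift runs from 0.136 × 0.20 = 0.027 to 0.383 × 0.30 = 0.115, roughly 3 to 11 percentage points. DBP is ignored, so this indicates size and is not a bound.

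**Step 4: effect on the arm difference.** Assume SD 12 and arm means 5 mm Hg apart.

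- *Means 130 and 125.* At 140 the control rates are Φ(0.833) = 0.798 and Φ(1.25) = 0.894, a difference of 9.7 points. At 130 they are 0.500 and Φ(0.417) = 0.662, a difference of 16.2 points. The higher cut-off shrinks the difference.
- *Means 140 and 135.* At 140 the difference is 0.662 − 0.500 = 16.2 points. At 130 it is Φ(−0.417) − Φ(−0.833) = 0.338 − 0.202 = 13.6 points. The higher cut-off widens it.

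The direction reverses when the midpoint of the two arm means passes 135.

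**The case against.** The best defence is that the age split is not confined to the office list. The withdrawal protocol in 7.3.2 gives 130/80 and 140/90 as the target for the study, and 9.2 matches it. The ABPM list sits under standard-arm management and is not stated as an outcome criterion. Objective 2 in section 4.2 names no instrument, so the reference to ABPM in 9.2 could itself be the drafting slip.

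This shows that the error could lie in either half of item 2, but it does not remove the conflict. The 7.3.2 statement names no instrument and supplies no age-specific ABPM limit, and the 7.3.1 list contains the only values labelled as ABPM limits. Nor is this a detail left to an analysis plan, because the protocol already fixes both instrument and cut-offs.

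It might also seem that item 2 leaves open which ambulatory mean is judged. That is a minor point. Item 1 of 9.2 refers back to the primary endpoint, and section 4.1 specifies 24-h ambulatory pressure, so the 24-h mean is the natural reading.

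Three stronger readings are tempting and are not supported:

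- *The rule biases the comparison or dilutes the treatment effect.* Both arms get the same rule, and Step 4 shows that the difference can shrink or widen. The protocol gives no expected 24-h level from which to claim a direction.
- *Control is overstated at all ages.* On the 24-h mean, the rules under 65 differ only at exact boundary values.
- *The endpoint lets one component alone qualify, for example 150/78.* The and/or wording is in the 7.3.1 targets, not in the 9.2 criteria.

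**Conclusion.** The inconsistency is real and does not depend on how the ABPM list is read. For patients aged 65 or over, 24-h means of 131-139/81-89 are controlled under 9.2 and above both of the protocol's own 24-h ABPM limits.

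Its scope is limited to one of eight secondary outcomes and the subset built on it for outcome 3. The consequence is misclassification and a control rate that is hard to interpret in older patients. The mismatch itself is certain from the text. The size (about 14-38% of older patients, roughly 3-11 points overall) rests entirely on the assumed SBP distribution and age share, and considers SBP alone. The point should be corrected but does not threaten the primary analysis.

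**What to change.** Reconcile 7.3.1, the target statement in 7.3.2 and item 2 of 9.2, so that the endpoint's instrument and cut-offs belong together. For endpoint scoring:

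1. Score ABPM control on the 24-h mean against the protocol's own 24-h ABPM limits, and state that both SBP and DBP must be met.
2. Report control on clinic BP by the age-split office cut-offs as a separate endpoint.
3. State which of the two defines the subset for outcome 3.
4. Name the instrument to which the 7.3.2 target refers.

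This concerns how the endpoint is scored and takes no view on treatment targets.

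The cost is a wording amendment, because ABPM and clinic BP are both already collected. There are two downsides. The reported ABPM control rate in older patients will be lower. And the endpoint limit will differ from the 7.3.2 target for those aged 65 or over unless that statement names its instrument.
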